3.3.5 Efficacy End Point: Ocular surface redness score

Ocular surface redness (nasal or temporal) will be assessed using the Validated Bulbar Redness grading scale (VBR).³⁹ The VBR consists of a set of ten images illustrating different degrees of ocular surface redness (OR), ranging from normal to severe, and each image is assigned a value in an order of ascending severity. Colored copies of these images will be made and put up in all the examination rooms. Subjects will be examined by a slit-lamp at 10X magnification using direct diffuse illumination (slit fully opened, angled at 30°- 50° approximately; at half illumination intensity with rheostat set to maximum voltage) and the bulbar conjunctival injection of the subject's eye (nasal and temporal) will be compared to the reference images and graded accordingly. To maintain uniformity, all subjects will be graded by a single physician (Principal Investigator) under constant illumination conditions. The subjects will be asked to look at nasal or temporal fixation marks while the physician will examine the temporal or nasal bulbar conjunctivae, respectively.

Photographic anchors and their respective grades for ocular surface redness are shown below:

[figure not shown]
3.3.6 Efficacy End Point: Keratograph Oculus Redness Score

Keratograph is FDA approved and is used in routine clinical care of patients in the US. The Oculus Keratograph 5M performs a non-invasive tear film analysis. It uses a Placido bowl with a camera aperture that has a fixation mark in the center. The device provides consistent illumination, allowing scanning of the exposed bulbar conjunctiva to take place. The keratograph then analyzes the scanned area. This system generates a BR score automatically, which is based on the area percentage ratio between the vessels and the rest of the analyzed area.

For instance, if the ratio is 16%, then the score is 1.6. The maximum ratio, according to the manufacturer, is 40%; therefore, the BR scores that the machine generates range between 0.0 and 4.0.

[figure not shown]
Non-invasive Keratograph Tear Film Break-up Time (NIKBUT)

The non-invasive Keratograph tear film break-up time (NIKBUT) measures tear film stability. The NIKBUT is automatically measured within seconds, without fluorescein application, Tear Break-up Time (TBUT) will be measured twice for each eye using IR video derived from the Oculus noninvasive Keratograph tear breakup time (NIKBUT) tool. Based on the device IR video, the device generates 2 measures for TBUT: NIKBUT-first (time at which the first breakup of tears occurs) and NIKBUT-average (average time of all breakup incidents) automatically and without touching the eye.

Tear Meniscus Height (TMH)

[figure not shown]
Tear Meniscus Height (TMH) Measurement evaluates the course of the tear meniscus along the eyelid by means of the new infrared illumination and precisely measure the tear meniscus height with an integrated ruler. The TMH is measured twice for each eye using IR images derived from the Oculus TMH tool, The TMH will be graded perpendicular to the lid margin at the central point relative to the pupil center. Oculus TMH measurement is generated automatically by Oculus K5M software. The tear meniscus measurement is important for determining the tear film quantity.

- Buttons for tear meniscus measurement
- 4 Examination and patient data

3.3.7 Efficacy End Point: TearLab Osmolarity Test

TearLab Osmolarity Test is FDA approved and is used in routine clinical care of patients in the US. The TearLab Osmolarity Test is intended to measure the osmolarity of human tears to aid in the diagnosis of dry eye disease in patients suspected of having dry eye disease. Abnormal tear osmolarity is a failure of homeostatic osmolarity regulation, a key feature of dry eye disease (DED). When left unchecked, hyperosmolar tears in early stage DED will lead to damage of the cornea and conjunctiva evident in later stage disease. The higher the osmolality, the more severe the dry eye. The TearLab Osmolarity Test provides a quick and simple method for determining tear osmolarity using nanoliter (nL) volumes of tear fluid collected directly from the eyelid margin. The TearLab Osmolarity Test utilizes a temperature-corrected impedance measurement to provide an indirect assessment of osmolarity. After applying a lot-specific calibration curve, osmolarity is calculated and displayed as a quantitative numerical value.

3.3.8 Efficacy End Point: InflammaDry for MMP-9 Protein

InflammaDry is FDA approved and is used in routine clinical care of patients in the US. Elevated levels of the MMP-9 protein in human tears will be detected visually, qualitatively, and in vitro using InflammaDry for MMP-9. InflammaDry will be performed PRIOR to instilling ocular anesthetic, topical dyes, or performing Schirmer testing. Tear fluid sample will be collected by gently dabbing the sampling fleece on the inside of the patient's palpebral conjunctiva a minimum of six to eight (6-8) dabs along the conjunctiva, afterwards allow the sampling fleece to rest against the conjunctiva for an additional five (5) seconds. Assemble the test by gently placing the sampling fleece of the sample collector into the sample transfer window of the test cassette body. Open the buffer vial and immerse the absorbent tip for a minimum of 20 seconds. Remove the absorbent tip from the buffer vial, replace the protective cap, and lay the test flat on a horizontal surface for ten (10) minutes.

The results of the test are indicated through two (2) lines, the control line and the result line in the result window.

POSITIVE RESULT: The presence of both a BLUE line in the control zone and a RED line in the result zone indicates a positive result. A positive result indicates the presence of MMP-9 >= 40 ng/ml.

NEGATIVE RESULT: The presence of only a BLUE line in the control zone indicates a negative result. A negative result is indicative of an MMP-9 < 40 ng/ml.

INVALID RESULT: If a BLUE line does not appear, the test may be invalid. Re-immerse the absorbent tip into the buffer vial for an additional ten (10) seconds. If a BLUE line still does not appear, the test must be discarded and the subject retested by resampling the eye using a new InflammaDry test.

[figure not shown]
3.3.9 Tolerability End Point: Test Substance Tolerance (Visual Analogue Scale)

Subjects will assess their tolerance to the administration of the test medication (placebo/ study drug), utilizing a Visual Analog Scale (VAS). The VAS is a 100 mm horizontal line with verbal descriptors at either end. The VAS ratings will be completed after administration of the test medication on Day 1 (post-dose), week 2, week 4, week 6 and week 8. Subjects will place a single slash mark across the horizontal line between the end labeled "completely intolerable" (0 mm) and "easily tolerable" (100mm). The VAS rating is as follows:

Please rate the degree of comfort or lack of comfort associated with administering the eye drop by making one slash mark on the line below:

Visual Analogue Scale

On the scale of 0 to 100 seen below, please mark where you would rate your tolerability to administration of the test drug.

3.4 Safety Endpoints

Safety assessments include Vital Signs, recording of all complications and adverse events, as well as ophthalmic exam findings. All ocular and non-ocular adverse events will be assessed for severity and relationship to the investigational product.

Primary safety endpoint:

• The proportion of subjects at week 8 who were able to successfully complete a full eight weeks of therapy with topical administration four times per day (q.i.d.)

Secondary safety endpoint:

- All adverse events reported, whether deemed related to treatment, or not.
- Clinically significant changes in vital signs or ophthalmic examination from baseline.

3.4.1 Vital Signs

Vital signs will be obtained and recorded at the Day 1 Visit, prior to the first administration of the test medication (placebo/ study drug) and on week 2, week 4, week 6, week 8 and week 10. The following vital signs will be measured: 1) blood pressure measurements (mm Hg) will be taken while the subject is relaxed in a sitting position for at least 3 minutes with the arm at heart level. 2) Heart rate will be measured via auscultation of the heart or palpation of a peripheral pulse and will be recorded in beats per minute (bpm). 3) Oral temperature will be recorded in degrees Fahrenheit (^{0}F). Subjects with an oral temperature less than (\leq) 99.6 ^{0}F (37.4 ^{0}C) may continue.

Clinically significant negative changes from baseline will be recorded on the adverse event forms.

3.4.2 Ophthalmic Examination

At all visits, the Investigator will conduct a complete undilated examination of the eyes using a binocular slit lamp. The Investigator will examine the tear film, eye lids, lashes, bulbar and palpebral conjunctiva, upper and lower lid puncta, cornea, anterior chamber, iris, lens, and anterior vitreous. Specific signs that will be recorded include: lacrimal sac area erythema, swelling or tenderness; froth or debris or mucous strands in tear film; eyelid hyperemia; punctal hyperemia or atresia; conjunctival/ episcleral hyperemia; papillary or follicular conjunctival reaction; chemosis, episcleral edema; superficial punctate keratopathy, corneal scar, corneal neovascularization; presence and number of corneal filaments, presence or absence of mucoid films, anterior chamber cell, flare or KPs; pupil shape abnormalities, anterior or posterior synechiae, iris neovascularization; lenticular opacities; vitreous cells or pigment. Conjunctival hyperemia (ocular surface redness) will be graded at each visit using the VBR grading system as explained in section 3.2.5. Measurements at first and last visit will include: visual acuity (BCSVA), manifest refraction and intraocular pressure measurement. Clinically significant changes from baseline examination will be recorded on the adverse event forms. Also, conjunctival and eyelid margin swabs will be taken for microbiologic cultures at baseline and at week 8 to assess potential changes in bacterial flora in a subset of participants (20 subjects each, in study and control groups). Because of the masking, selection of subjects for conjunctival cultures will be made by the pharmacist incharge for randomization.

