1.3 Preclinical Data

We have performed investigations to show that eDNA, NETs, and neutrophils are present on the ocular surface in oGVHD patients and abundant in mucoid films. We showed that eDNA and NETs are present in excessive amounts on the ocular surface of patients with severe, tear-deficient dry eyes. Among all patients with dry eyes, those with GVHD had the highest eDNA amount in their tear fluid. Expression of genes downstream of eDNA signaling, such as TLR9, MyD88, and type I interferon, as well as the inflammatory cytokines, interleukin-6 and tumor necrosis factor alpha, was also significantly increased in dry eyes patients. Immunolocalization experiments revealed that the molecular components of NETs include histones, cathelicidin, and neutrophil elastase. Next, using a FRET-based assay, we found that tear fluid nuclease activity was reduced in dry eyes patients. We determined that the normal concentration of DNase I in tear fluid is 3.14 ng/ml, similar to that in serum and saliva.

Taken together, these findings suggest that in healthy eyes, eDNA is produced in the precorneal tear film and cleared by tear fluid nucleases. In patients with severe dry eyes, tear fluid nuclease deficiency allows eDNA, neutrophils, and NETs to accumulate in the precorneal tear film and cause ocular surface inflammation. The practical implication of our findings is the suggestion of new therapeutic interventions based on clearing eDNA, NETs, and their molecular components from the ocular surface, as well as inhibiting eDNA signaling pathway gene expression. DNase I, an enzyme which selectively cleaves DNA, is one such therapeutic intervention. These findings have been published in Investigative Ophthalmology and Visual Sciences, 24,25 and were quoted as a new insight into dry eye inflammation by an editorial comment in the same publication. Serum tear eye drops (containing DNase I) have been topically applied to the eye with significant therapeutic benefit to patients with severe dry eyes, including patients with oGVHD. These findings underpin the basis of this research protocol.

Our data reveals that patients with oGVHD are significantly more symptomatic with greater severity of clinical signs and higher tear fluid eDNA amount as compared to other tear-deficient dry eye disease subtypes, 25 therefore patients with oGVHD are ideal candidates for investigating clinical benefit that may result from clearing eDNA and NETs.

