3.3 Secondary Study Endpoints

The secondary study endpoints will include:

- 1. The change in the Ocular Surface Disease Index (OSDI) which is a patient's subjective rating scale
- 2. Change in tear secretion as measured by Schirmer I test
- 3. The proportion of eyes achieving complete corneal staining clearance after treatment
- 4. Change in conjunctival surface staining score as measured by Fluorescein and Lissamine dye staining
- 5. The change in subjective ocular surface redness score (OR) using the validated bulbar redness (VBR) grading scale
- 6. Visual acuity change
- 7. Change in frequency of administration of artificial tears or concomitant eye drops
- 8. Change in number of corneal filaments (slit-lamp examination)
- 9. Change in amount of mucoid films (slit-lamp examination)
- 10. Clinical Global Impression (CGI) of change in symptoms from baseline (physician's rating)
- 11. Subject Global Assessment (SGA) of overall change from baseline (subject's rating)
- 12. Change in Non-Invasive Keratograph Tear Break-Up Time (NIKBUT)
- 13. Change in Tear Meniscus Height (TMH)
- 14. Change in Keratograph Ocular Bulbar Redness Score
- 15. Change in MMP-9 Protein Detection
- 16. Change in Tear Fluid Osmolarity
- 17. Change in eDNA abundance in tear fluid
- 18. Change in tear fluid cell count
- 19. Change in eDNA strand length on Schirmer test strip impressions

Corneal filaments are mucous tags that are adherent to the surface of cornea. Mucoid films are mucous collections accumulating on the surface of the eye. The number of such mucus tags/ filaments will be counted on each clinical examination (slit-lamp examination).

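### Secondary endpoint 9 is a change in the amount of mucoid films, but the protocol text records only whether films are there, so a partial reduction cannot be computed

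*Combined protocol and SAP*

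**What the plan says.** Protocol section 3.3 lists two neighbouring slit-lamp endpoints: number 8, "Change in number of corneal filaments (slit-lamp examination", and number 9, "Change in amount of mucoid films (slit-lamp examination". The text under the list defines the two findings separately: "Corneal filaments are mucous tags that are adherent to the surface of cornea" and "Mucoid films are mucous collections accumulating on the surface of the eye". It then adds: "The number of such mucus tags/ filaments will be counted on each clinical examination (slit-lamp examination".

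Section 3.4.2 lists the signs to be recorded at the slit lamp, among them "presence and number of corneal filaments, presence or absence of mucoid films". The visit lists in 6.5.1 to 6.5.7 name the slit-lamp examination without saying how any sign is scored. Section 7.2 chooses the model by variable type (continuous, ordinal or nominal) and assigns no type to mucoid films.

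**The concern.** An endpoint defined as a change in amount needs a quantity at baseline and again at follow-up. The recording instruction supplies a quantity for filaments and, in the same phrase, only a yes or no for films. Endpoint 8 therefore has matching data and endpoint 9 does not.

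Films sit close to the trial's mechanism. Section 1.3 reports that "eDNA, NETs, and neutrophils are present on the ocular surface in oGVHD patients and abundant in mucoid films", and the drug is meant to clear eDNA and NETs. In a Phase I/II trial looking for preliminary efficacy, a graded reading at the same examination could be informative. Once the entries are yes or no, the grade cannot be recovered from them. The analyst would also have to decide after the fact what kind of variable endpoint 9 is.

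**Working it through.** The plan states no figure for mucoid films, so there is none to reproduce. The 30 per group in 7.1 (36 to be enrolled) is derived from corneal staining and does not bear on this point.

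**Step 1. Endpoint against record.**

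| Finding | Endpoint (3.3) | Recorded (3.4.2) | Derivable? |
|---|---|---|---|
| Corneal filaments | 8: change in number | Presence and a number | Yes |
| Mucoid films | 9: change in amount | Yes or no | Amount: no. Appearance or disappearance: yes |

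**Step 2. Is an amount supplied elsewhere?**

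- The counting sentence in 3.3 names tags/filaments. Tags are what 3.3 calls filaments, and films are defined apart from them.
- Section 3.4.2 also lists "froth or debris or mucous strands in tear film". This is a separate sign with no scale.
- Question 2 of the Subject Global Assessment (3.3.4) is the subject's own five-point rating of mucous strings or discharge. It belongs to endpoint 11 and is not a slit-lamp measure.
- No grade, area or count for films appears in the visit lists or in 7.2.

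**Step 3. What a yes/no record can show.** Code absent as 0 and present as 1. Change = follow-up minus baseline, which can only be −1, 0 or +1.

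Compare a four-level grade (0 none to 3 heavy). It has 4 × 4 = 16 baseline/follow-up pairs: 4 unchanged, 6 improvements and 6 worsenings.

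- Improvements: the yes/no record shows 3 of the 6 (3→0, 2→0, 1→0). The other 3 (3→2, 3→1, 2→1) are present at both visits.
- Worsenings: it shows 3 of the 6 (0→1, 0→2, 0→3). The other 3 (1→2, 1→3, 2→3) are present at both visits.

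These are counts of possible patterns, not of patients. How often each occurs is not known from the documents.

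**Step 4. Direction of the loss, on assumed rates only.** Assume films at baseline in all 36 eyes per arm, and any reduction in 60% on drug against 25% on vehicle. None of these rates is in the documents. With p̄ the mean of p1 and p2,

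power = Φ{ (|p1 − p2| − 1.96·√[2p̄(1 − p̄)/n]) / √[(p1(1 − p1) + p2(1 − p2))/n] }.

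For 0.60 against 0.25: p̄ = 0.425, the two standard errors are 0.1165 and 0.1090, and (0.35 − 0.2284)/0.1090 = 1.116, so power is about 87%.

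| What is scored | Drug | Vehicle | Power |
|---|---|---|---|
| Every reduction | 60% | 25% | 87% |
| Complete clearance only (about two thirds of reductions) | 40% | 17% | 58% |
| Complete clearance only (about half) | 30% | 12% | 47% |
| Complete clearance only (about one third) | 20% | 8% | 31% |

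This shows only that power falls as more of the response is partial. If nearly all reductions were complete, little would be lost.

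**The case against.** The strongest reply has three parts.

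1. The list in 3.4.2 is open-ended, sits under the safety endpoints and is not a scoring rule for an efficacy endpoint. The CRF is not among the documents and may carry a grade. This stands as a limit: the finding is about the protocol text, and it cannot be said that graded data are in fact being lost. It does not remove the mismatch, because a graded CRF field would itself disagree with 3.4.2.

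2. The counting sentence follows the definitions of both filaments and films, so it might reach back to both. The literal reading is narrower. The broader one would contradict 3.4.2, so the two sections would still need reconciling.

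3. A response short of clearance would not go wholly unseen. Endpoints 17 to 19 measure tear eDNA, cell count and eDNA strand length, and subjects rate their own mucus on a five-point scale. This stands, and it lowers the stakes. None of these is a slit-lamp film amount.

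Three stronger readings are tempting but not supported.

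- A reader might size the loss as an assumed film prevalence times 36 per arm: 36 × 0.30 = 11 to 36 × 0.90 = 32 eyes able to improve. An eye without film cannot improve on any scale, so that ceiling is the same with a grade and does not measure this defect.
- A reader might infer that shrinkage without clearance is the likeliest early drug effect. The only clinical experience with the eye drops is one case report (1.4). It describes mucoid strands decreasing and gives no film grades.
- A reader might conclude that films cannot be analysed at all. A yes/no version can be.

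**Conclusion.** The mismatch is real. Endpoint 9 as worded cannot be computed from the recording the protocol specifies, and a film that shrinks or grows while persisting is recorded the same at both visits. This rests on the text of 3.3 and 3.4.2 and on nothing else in the documents supplying an amount; it assumes that the CRF follows 3.4.2.

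The size of the loss cannot be stated, because the documents give no prevalence and no partial-response rate. The power figures above illustrate direction under assumed rates and are not estimates for this trial. The issue touches one of 19 secondary endpoints. The primary efficacy, tolerability and safety endpoints and the sample size are unaffected. It is worth correcting because the correction is cheap and yes/no entries cannot be regraded later.

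**What to change.** - **Preferred.** In 3.4.2 and on the CRF, replace the yes/no entry for films with a prespecified ordinal amount for each eye at each slit-lamp examination, with fixed descriptors (for example 0 none, 1 trace, 2 moderate, 3 heavy). State in 7.2 that endpoint 9 is ordinal and uses the mixed-effects ordinal logistic model already named there.
- **If the CRF already has a graded field.** Align 3.4.2 with it and state the scale.
- **If grading is not wanted.** Restate endpoint 9 as change in presence or absence of films in all target eyes, analysed with a mixed-effects logistic model. Keep all target eyes: limiting the analysis to eyes with films at baseline would drop the rest and hide newly appearing films. This option makes endpoint and data agree but still does not register partial reduction.

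The cost is one CRF item and one line of protocol text, plus a line in 7.2 naming the variable type. The examination and the examiner stay the same. The drawback of the preferred option is that the grade is unvalidated.

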	8.5.		
	8.6	ADVERSE EVENT REPORTING	
	8.6.		
	8.6.		
	8.6.	-	
	0.0.	8.6.3.1 FOLLOW-UP INFORMATION	
	8.7	STUDY CLOSE-OUT	
	8.7		
	0.7	8.7.1.1 7 CALENDER DAY TELEPHONE OR FAX REPORT.	
		8.7.1.2 15 CALENDER DAY WRITTEN REPORT	
	8.8	FAX NUMBER FOR IND SAFETY REPORTS.	
	8.9	IN CASE OF EMERGENCY	
	8.10	DATA SAFETY MANAGEMENT PLAN	
	8.11	STUDY OVERSIGHT	_
	8.12	REPORTING CHANGES IN STUDY STATUS	
9	DAT	A QUALITY AND SAFETY REVIEW PLAN AND MONITORING	39
	9.1	DATA QUALITY AND MANAGEMENT	39
	9.1	-	
	9.1		
	9.2	SUBJECT ACCRUAL AND COMPLIANCE	
	9.2		

	9.2	2.2 MEASUREMENT AND REPORTING OF PARTICIPANT ADHERENCE TO TREATMENT PROTOCOL	40
g	9.3	STOPPING RULE	40
	9.4	DATA AND SAFETY MONITORING BOARD (DSMB)	40
	9.4		
9	. 5	SAFETY REVIEW PLAN	41
10	CON	NFIDENTIALITY	41
11	sou	JRCE DOCUMENTS	42
1	1.1	RECORDS RETENTION	42
12	ETH	ICAL CONSIDERATIONS	42
13	STU	DY FINANCES	
1	3.1	FUNDING SOURCE CONFLICT OF INTEREST	43
1	3.2	CONFLICT OF INTEREST.	43
1	3.3	SUBJECT STIPENDS OR PAYMENTS	43
14	REF	ERENCES	44
15	APP	ENDIX I	47

SCHEDULE OF VISITS AND PROCEDURES

	gı	(e)	(es)					
	Screening	Day 1 (Pre-Dose)	Day 1 (Post-Dose)	Week 2	Week 4	Week 6	Week 8	Week 10
Informed consent	Х							
Demographic information	Χ							
Medical history/ Con Meds/ Transplant history	Х							
Ophthalmic/ oGVHD history	Χ							
Vital signs		Х		Χ	Χ	X	Χ	Х
Best Spectacle Corrected Visual Acuity		Х						Х
Ocular Surface Disease Index (OSDI)	X	Х		Χ	Χ	X	Χ	Х
Clinical Global Impression (CGI)				Χ	Χ	Х	Χ	Х
Subject Global Assessment (SGA)				Χ	Χ	Χ	Χ	Х
Visual Analogue Scale (VAS)			Х	Х	Х	Х	Х	
Ophthalmic examination (Slit lamp)	Χ	Х		Χ	Χ	Х	Χ	Х
Schirmer 1 test and Fluorescein and Lissamine Dye staining	Х	Х					Х	
Ocular surface Redness (OR) score		Х		Χ	Χ	Χ	Χ	Х
Tear fluid analysis (PicoGreen, Cellometry)		Х					Χ	
Keratograph Oculus Redness Score		Χ			Χ		Χ	
Non-invasive Keratography Tear Film Break-up Time (NIKBUT)		Х			Χ		Χ	
Tear Meniscus Height (TMH)		Χ			Χ		Χ	
TearLab Osmolarity Test		Х			Χ		Χ	
InflammaDry for MMP-9 Protein		Х			Х		Х	
Pregnancy test (urine)*	Х							
Randomization visit		Х						
First study medication		Х						
Drug dispensation visits			Х	Х	Х	Х		
Instruction on study medication self- administration			Х	Х	Х	Х		

Version: 10.0; 07-26-2018

Physical inspection of nose & oropharynx	Х		Х	Х	Х	Х	Х
Adverse Events/ Concomitant Medications	Х	X++	Х	Х	Х	Х	Х
Conjunctival culture**	Х					Х	

^{*}If applicable ++ AEs only

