1.5 Dose Rationale and Risk/Benefits

RhDNase I 1mg/ml (0.1%) will be applied topically to the ocular surface as eye drops. This is the same dose as is currently in use in patients with Cystic Fibrosis. The drug formulation is being used unchanged. This dose has been effective in reducing eDNA content when given to patients with cystic fibrosis. We do not expect any serious adverse events with this dose.

Drugs are routinely applied topically to the ocular surface as eye drops because of easy access to the ocular tissues and good drug bioavailability. Therefore, we will use rhDNase I topically. Since rhDNase I does not accumulate in tissues and its enzymatic activity is expected to be short-lived, we have elected to use the eye drops four times a day. The ocular residence time for emulsion eye drops (e.g. Restasis, used twice a day) has been estimated as approximately 2 hours.³³ We expect even shorter ocular residence time for rhDNase I, given the lower viscosity of its vehicle. Future clinical trials will be needed to assess whether lower frequency of dosing is also effective. The feasibility of performing this trial would have been suspect if we had included more than one dosing in this trial because of the much larger number of oGVHD patients needed.

Since rhDNase I is not expected to increase the production of natural DNase I, but rather it only supplements it so that the imbalance of decreased tear fluid DNase I is corrected, we expect long-term use of rhDNase I. Thus, we have chosen an eight weeks duration of therapy as it will give us better data to predict side effects during long-term use.

RhDNase I is currently used as an inhaled drug in adults and children with cystic fibrosis. Patients with cystic fibrosis have experienced a change in or loss of their voice, discomfort in the throat, chest pain, red watery eyes, rash, dizziness, fever, or runny nose. Most of these are systemic side-effects that are not generally seen with eye drops. These side effects are usually mild and short-lived.

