3.1 General Design

This will be a Randomized controlled trial, in which a total of 72 subjects will be enrolled at 1 clinical site. Subjects will be randomly assigned to one of two groups (#1, #2), with 36 subjects per group. One group will be given placebo (Vehicle eye drops) and the other group will be given eye drops containing the study drug (rhDNase I 0.1%).

Patients with established oGVHD will be approached by a member of the research staff to determine if he/ she might be interested in participating in a research study. If the subject is interested, the research staff member will describe the study. If the subject is willing to enter the study, the study will be discussed and the subject will be asked to sign the informed consent form. Consent will be obtained prior to screening to determine eligibility. Screening procedures include documentation of definite oGVHD. Eligible subjects will be enrolled in the study.

All enrolled subjects will receive their first dose of test medication (placebo/ study drug) on study Day 1 in the doctor's office, and after completion of the study assessments, will have the topical eye drops dispensed for self-administration. See Section 5.4 *Preparation and Administration of Study Drug* for details.

Subjects will be provided with diaries to record the time of each dose and will also be asked to record any adverse symptoms. In addition, they will be asked to make a note of any missed doses together with the reason for the omission. Subjects will return two weeks later on Day 14 for further study assessments, thereafter at 4 weeks, 6 weeks and 8 weeks (the last day of treatment), and again at 10 weeks after two weeks of no treatment with study drug for the final study assessments.

Because NETs have an important role in the innate defense against microbes,³⁵ treatment with DNase I to clear NETs may increase susceptibility to ocular surface infections. Symptom relief is an important goal in patients having dry eyes, with the proviso that treatment does not interfere with pathogen defense. Therefore, we will determine whether DNase I treatment affects the ocular surface microbiome.

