6.5.6 Visit 6: Week 8 (± 2 days)

Treatment Visit (after any dose for that day)

- Vital Signs
- OSDI
- Fluorescein and Lissamine Dye staining, and Schirmer 1 test
- Keratograph Oculus Redness Score
 - > Non-invasive Keratography Tear Film Break-up Time (NIKBUT)
 - > Tear Meniscus Height (TMH)
- TearLab Osmolarity Test
- InflammaDry Test for MMP-9 Protein
- Clinical Global Impression, Subject Global Assessment
- Test Substance Tolerance (VAS)
- Ophthalmic Examination (slit lamp examination, Ocular surface redness score)
- Tear fluid collection for analysis (PicoGreen, Cellometry)
- Physical Inspection of the Nose and Oropharynx
- Conjunctival and eyelid margin cultures
- Review the subject's diary and record changes in concomitant medication, deviations from drug schedule and adverse events.

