6.5.7 Visit 7: Week 10 (± 2 days)

Follow-Up Visit

- Vital Signs
- BSCVA (Snellen's chart)
- OSDI
- Clinical Global Impression, Subject Global Assessment
- Ophthalmic Examination (slit lamp examination, Ocular surface redness score)
- Physical Inspection of the Nose and Oropharynx
- Record changes in concomitant medication and adverse events.

7 Statistical Plan

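### No objective on-treatment measurement of visual acuity or eye pressure is scheduled, and the pressure and refraction measurements required by section 3.4.2 appear in no visit list

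*Combined protocol and SAP*

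**What the plan says.** Section 3.3 lists visual acuity change as secondary endpoint 6 and gives no time point. Section 3.4 makes "Clinically significant changes in vital signs or ophthalmic examination from baseline" a secondary safety endpoint.

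Section 3.4.2 sets the content of the eye examination and adds: "Measurements at first and last visit will include: visual acuity (BCSVA), manifest refraction and intraocular pressure measurement".

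The schedule table has a row for "Best Spectacle Corrected Visual Acuity", marked at Day 1 pre-dose and at Week 10. It has no row for intraocular pressure (IOP) or manifest refraction. The visit lists agree with the table: sections 6.5.2 (Day 1) and 6.5.7 (Week 10) include acuity, and the lists for Weeks 2, 4, 6 and 8 do not. At Week 8, the last treatment visit, the eye-examination entry reads "Ophthalmic Examination (slit lamp examination, Ocular surface redness score", and its bracket closes there.

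Section 3.1 has subjects return "again at 10 weeks after two weeks of no treatment with study drug for the final study assessments".

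**The concern.** Endpoint 6 is meant to describe what happens to vision under treatment, but its only scheduled post-baseline value is taken after treatment has stopped. An improvement or a loss that reverses on stopping could be absent from the data. Section 1.5 justifies the eight-week course by the wish to predict side effects of long-term use, and an on-treatment value serves that purpose better.

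For IOP and refraction the problem is a contradiction within the protocol. One section requires them, while the table and lists that a site works from omit them. The protocol itself treats pressure as relevant: section 1.4 cites the absence of pressure change in its one treated patient as evidence of tolerability. If the lists are followed literally, the ophthalmic-examination safety endpoint has no pressure data at any time.

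**Working it through.** The plan gives no figure on this point. Its one computed figure is the sample size in section 7.1, which reproduces: difference 3.1 − 1.24 = 1.86, standard deviation 2.5, two-sided 0.05, 80% power, noncentral t gives 29.35, rounded up to 30 per group. It does not enter the argument. The check here is a count and some date arithmetic.

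**1. Where each measurement is listed** (schedule table and sections 6.5.1 to 6.5.7)

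| Measurement | Section 3.4.2 | Schedule table | Visit lists |
|---|---|---|---|
| Visual acuity | first and last visit | Day 1 pre-dose, Week 10 | Day 1, Week 10 |
| IOP | first and last visit | no row | 0 of 7 |
| Manifest refraction | first and last visit | no row | 0 of 7 |

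On-treatment visits after Day 1 are Weeks 2, 4, 6 and 8. Acuity is listed at 0 of these 4.

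**2. Time between the end-of-treatment visit and the only follow-up acuity**

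Week 8 is day 56 ± 2 and Week 10 is day 70 ± 2.

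- Nominal: 70 − 56 = 14 days.
- Shortest: (70 − 2) − (56 + 2) = 10 days.
- Longest: (70 + 2) − (56 − 2) = 18 days.

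**3. Comparison with the other secondary endpoints**

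Staining, Schirmer test and tear-fluid assays are repeated at Week 8. Keratograph measures, osmolarity and MMP-9 are repeated at Weeks 4 and 8. Symptom index, redness, both global ratings, slit-lamp findings and the review of concomitant drops occur at every on-treatment visit. Of the 19 secondary endpoints in section 3.3, acuity is the only one with no scheduled on-treatment assessment.

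**4. Consequence for the analysis**

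Section 7.2 models treatment, time and their interaction. For acuity the scheduled times are Day 1 and Week 10, so the treatment-by-time contrast compares baseline with an off-drug value. Section 4.4.2 asks subjects who withdraw before Week 8 to complete the Week 10 procedures as soon as possible. Their acuity may be taken close to the last dose, while completers are measured about two weeks after it. The follow-up values therefore mix two states.

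**5. What the first and last visit means**

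Visit 1 is screening, and its list has no acuity. Baseline acuity is at Visit 2. The last visit could be Week 10, as the acuity row implies, or Week 8: section 3.4.3 places tear sampling at the first and last treatment visits, which the lists show as Day 1 and Week 8. Section 3.4.2 does not say which it means.

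**The case against.** The strongest reply is that the plan is not blind to vision or pressure during treatment.

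- A change that persists would show in the Week 10 acuity.
- Subjects who withdraw before Week 8, among whom a harmful change is most likely, are asked to have the Week 10 procedures promptly, and these include acuity.
- The symptom index has items on blurred and poor vision and is completed at Weeks 2, 4, 6 and 8.
- A slit-lamp examination and adverse event review take place at each treatment visit, and section 5.6 provides for interim visits when symptoms occur.

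All of this stands. A reader might infer that on-treatment changes in vision or pressure cannot be detected at all; the documents do not support that. What remains is that none of these provisions measures acuity or pressure on treatment in a subject who completes the course.

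Three other tempting readings also fail.

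- A reader might take section 1.5, where the drug's "its enzymatic activity is expected to be short-lived", to mean that the sponsor expects any acuity effect to be gone by Week 10. That phrase justifies four-times-daily dosing and is followed by a discussion of ocular residence time in hours. It gives no rate at which a clinical effect would fade.
- A reader might use concomitant corticosteroids as the reason to measure pressure before Week 10. Section 6.5.1 has subjects continue them throughout the study, so a steroid-related rise is not tied to stopping study drug, and a Week 10 reading could still show it.
- A reader might conclude that pressure will not be collected. Section 3.4.2 does require it, so the finding is an inconsistency, not proof of non-collection.

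It is also fair that taking acuity at the first and last visit is a design choice, and that acuity is one of 19 secondary endpoints.

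**Conclusion.** The point holds in a limited form. No objective on-treatment acuity or IOP measurement is scheduled. After baseline, acuity is scheduled once, nominally 14 days (10 to 18) after the Week 8 visit, so a change that reverses within that interval could be missed in subjects who complete treatment. How likely such a reversal is cannot be judged from the documents.

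For IOP and refraction the outcome depends on which text the site follows. Under the visit lists there is neither a baseline nor a follow-up value, and even a persistent pressure change could go unrecorded. Under section 3.4.2, with the last visit read as Week 10, there is one follow-up value, taken off drug.

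The weight is moderate: one secondary efficacy endpoint and part of one secondary safety endpoint are affected. The primary efficacy and tolerability endpoints, the sample size and the error rates do not change.

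**What to change.** 1. Add best spectacle corrected acuity to the Week 8 column of the schedule table and to section 6.5.6. Keep the Week 10 measurement as the off-drug follow-up. State in sections 3.3 and 7.2 that Week 8 is the analysis time for endpoint 6.
2. Reconcile section 3.4.2 with the schedule table and section 6.5. List IOP and manifest refraction explicitly, define the first visit as Day 1 pre-dose (where baseline acuity is taken), and say which visit is the last.
3. Preferably take the post-baseline IOP at Week 8, while subjects are still on treatment. Section 4.4.2 sends early withdrawals to the Week 10 procedures, so IOP should also be in that list, or be named in section 4.4.2.

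The cost is a set of schedule edits and a few extra minutes at a visit that already takes place. IOP and refraction are measurements that the protocol already requires.
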